**Secondary:**

- To assess the safety profile expressed in terms of incidence of >grade 3 toxicity or proportion of patients developing > grade 3 in metastatic neuroendocrine tumors who have progressed on Lu-177 DOTATATE PRRT.

**3. Study End-point:** Safety and efficacy assessment**4. Study Design:** Phase II (Simon Two Stage), Interventional, Single Arm, Open Label**5. Study Sites:** Departments of Nuclear Medicine, TMH, Parel and RRU, ACTREC**6. Pre-screening:** Patients of metastatic NET who have progressed on Lu-177

DOTATATE PRRT will be referred after discussion in Neuroendocrine Tumor Clinic, TMH or HPB-UGI Clinic at RRU, ACTREC.

**7. Screening:** Patients will be confirmed for disease progression on Ga-68 DOTATATE and/or FDG PET/CT imaging.**8. Inclusion Criteria:**

- Male or female, age greater than 18 years
- Histopathological diagnosis of well-differentiated GEP-NET
- Positive Ga-68-DOTANOC PET/CT, Krennigs score  $\geq 3$
- Locally advanced/inoperable disease or metastatic disease
- Patient who have shown disease progression with Lu-177 DOTATATE PRRT

- Karnofsky performance-status score of at least 60 or ECOG performance status </=2
- Life expectancy greater than 6 months

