- c.** Clinical and Quality of Life Assessment using EORTC QLQ C30 questionnaire before therapy, at 4 weeks and 8 weeks after each therapy session.
- d.** Imaging Follow-up (as per established institutional standard-of-care) as follows: Ga-68 DOTANOC PET/CT will be performed at 4-6 weeks after each therapy session for documentation of response. After completion of protocol treatment, patients will be followed up as per standard institutional practices.

**13. Study Duration:** 2 years

**14. Follow-up Period:** 1 year

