**15. Study Assessments:**

**Response assessment:** Disease control rate will be measured as a primary endpoint. It is percentage of patients achieving complete or partial response or stable disease on Ga-68 DOTATATE PET/CT. Response assessment will be done using RECIST 1.1 for solid tumors. Non-PD (non-disease progression) after one session of Tb-161 therapy will be eligible for the second session. Patients showing CR with no

residual measurable disease will not undergo a second session of therapy. Patients with PD after 1 cycle of Tb-161 DOTATATE therapy will not continue in the study and will be referred to NET Clinic for further management. Currently there is no standard of care for treatment of refractory NET.

**Safety Assessment:** At each visit, the investigator will evaluate the subject to determine whether any AEs have occurred. CBC, LFT, RFT, Serum electrolytes will be done at 2 weeks, 4 weeks and 6 weeks after each therapy. AEs may be directly observed, reported spontaneously by the subject or by questioning the subject at each study visit. All laboratory values will be evaluated by the Investigator as to clinical significance. All post-baseline abnormal laboratory values considered clinically significant by the Investigator will be recorded as an AE. The NCI Common Terminology Criteria for Adverse Events version 5 (NCI CTCAE v5.0) will be used to classify and grade the intensity of adverse events during and after each treatment cycle. CTCAE will be used to grade all events regardless of attribution, in order to ensure objective reporting, and in order to report trial data according to accepted international guidelines. The highest grade of each observed toxicity will be recorded. The results will be computed in a tabular form in which the proportion of people having their highest grade of toxicity will be charted.

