**22. Reimbursement:** The study budget shall include costs of blood investigations and imaging studies, Tb-161 therapy and post-therapy dosimetry scanning. Patients study visits will also be budgeted in the study.

**23. Compensation:** It will be as per the Institutional IEC policy

**24. Evaluation of Benefits and Risks/Discomforts:** There is potential benefit in the form of improved survival and quality of life from this study. No potential physical, psychological or social risks. There are no alternate treatment possible during the study

**25. Risks/Benefits Analysis:** The study poses minimal risk, i.e. the probability and magnitude of harm or discomfort anticipated in the research are not greater in and of themselves than those ordinarily encountered in daily life or during the performance of

routine physical or psychological examinations or tests.

**26. Consent and Assent Process and Documentation:** Consent shall be taken after giving adequate time to the patient and Legally Accepted Representative to understand the study design. Consent shall be signed and dated by the patient and countersigned by the investigator. **A copy of the consent shall be handed over to the patient and one copy shall be kept for records.** Impartial witnesses shall be present to overlook the consent administration process. Participants' right to refuse to participate in the trial shall be respected. After the participant has entered into the trial, the clinician shall give alternative treatment to that specified in the protocol, at any stage, if he/she feels it to be in the best interest of the participant. The reason for doing so, shall be recorded; the participant will remain within the trial for the purpose of follow-up and for data analysis by the treatment option to which they have been allocated.

Similarly, the participant must remain free to change their mind at any time about the protocol treatment and trial follow-up without giving a reason and without prejudicing his/her further treatment. Patients who are not able to give consent won't be included in the study. In case a patient loses his/her ability to give consent during the study, he/she will be dropped out of the study.

**27. Trial closure:** The trial will close when all patients have completed follow-up. Details about reporting of trial closure to the regulatory and ethical committees.

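### Section 15 takes patients who progress after cycle 1 out of the study, while Section 26 and the blood-test schedule keep them in, so their later safety data are left uncertain

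*Protocol*

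**What the plan says.** Four parts of the protocol bear on a patient whose disease progresses after the first cycle.

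- **Section 15, response assessment.** Patients with PD after one cycle "will not continue in the study and will be referred to NET Clinic for further management". The sentence just before it deals with complete responders who have no residual measurable disease. It says only that they are not given a second session.
- **Section 26.** Once a participant has entered the trial, "the clinician shall give alternative treatment to that specified in the protocol, at any stage", if this is judged to be in the participant's best interest. The participant then "will remain within the trial for the purpose of follow-up and for data analysis by the treatment option to which they have been allocated".
- **Section 15, safety assessment, and Section 12(a).** "CBC, LFT, RFT, Serum electrolytes will be done at 2 weeks, 4 weeks and 6 weeks after each therapy". Neither place makes an exception for PD.
- **Section 12(d).** "Ga-68 DOTANOC PET/CT will be performed at 4-6 weeks after each therapy session for documentation of response".

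Section 2 gives one secondary objective: "To assess the safety profile expressed in terms of incidence of >grade 3 toxicity" (or the matching proportion of patients). Section 14 sets a follow-up period of one year. Section 27 closes the trial once every patient has completed follow-up.

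**The concern.** A patient who progresses after cycle 1 and is then treated with something else meets the description in Section 15 and can meet the one in Section 26. The first takes the patient out of the study. The second keeps the patient in for follow-up and analysis. No sentence gives either section priority, so two sites, or two investigators at one site, could act differently and both be following the protocol.

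The loss would fall on safety. If Section 15 is followed to the letter, observation stops at or soon after the scan that shows progression, before the scheduled toxicity window has necessarily closed. The patients cut short are not a random subset: they are the ones whose disease progressed. With 20 patients and toxicity as the only secondary objective, a few incomplete safety records matter.

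**Working it through.** The protocol gives no figure of its own on this point. The check sets the timetable against the exit rule, then limits the number of patients concerned.

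**Step 1. What can be lost after cycle 1.**

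| Item | Source | Scheduled | If the patient leaves at a scan before week 6 |
|---|---|---|---|
| Response scan | Section 12(d) | weeks 4-6 | done; triggers exit |
| Blood tests | Sections 12(a), 15 | weeks 2, 4, 6 | week 6 lost: 1 of 3 |
| Quality of life | Section 12(c): "before therapy, at 4 weeks and 8 weeks after each therapy session" | weeks 4, 8 after therapy | week 8 lost: 1 of 2 |
| Follow-up | Section 14 | 1 year | remainder lost |

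If the scan is done at week 6, the week-6 bloods may already have been taken. Quality of life is not among the objectives in Section 2, so its loss does not touch the secondary objective. Section 14 does not say when the year starts, so I do not put the lost follow-up into weeks.

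**Step 2. Effect on DCR.** Section 15 defines DCR thus: "It is percentage of patients achieving complete or partial response or stable disease on Ga-68 DOTATATE PET/CT". PD is none of these. A cycle-1 progressor is therefore a failure whether or not follow-up continues, provided the patient stays in the denominator of 20 that Section 16 fixes.

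**Step 3. Effect on the safety proportion.** Section 15 records the highest grade of each toxicity. A maximum over a longer period cannot be lower than over a shorter one. If a progressor stays in the denominator but is observed for less time, the proportion with high-grade toxicity can only be unchanged or understated. One missed event in 20 patients is 1/20 = 5 percentage points. If progressors were also removed from the denominator, the direction would be unknown.

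**Step 4. How many patients.** Every cycle-1 progressor is a DCR failure, but not every failure is a cycle-1 progressor, since some progress only after cycle 2. So the expected number of cycle-1 progressors is at most 20 × (1 − DCR), with the two rates in Section 16:

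- at 87%: 20 × (1 − 0.87) = 20 × 0.13 = 2.6
- at 67%: 20 × (1 − 0.67) = 20 × 0.33 = 6.6

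These are upper limits for a trial that accrues all 20 patients. The lower limit is 0. The documents give no split of failures between the two cycles.

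**The case against.** The best defence is that there is no true conflict. Section 26 does not name progressors. It concerns a clinician who departs from the protocol, whereas referral of a cycle-1 progressor to the NET Clinic is what the protocol itself prescribes. The Section 15 sentence stands among the rules on who receives a second session, so it may mean only that study treatment ends. Section 15 does not say that these patients leave the analysis. Section 12 says that patients are followed while they receive active cancer treatment, and the blood schedule has no exception for PD. A careful team might well collect the week-6 bloods anyway.

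Part of this stands. The milder reading is possible, and the blood schedule supports it, so this is a matter of reconciling text and not a design failure. The defence is not complete, however. For complete responders the neighbouring sentence speaks of withholding a session; for PD it speaks of leaving the study, so the difference in wording looks meant. Section 26 applies at any stage and does not exclude progressors. Section 12(b) ties later follow-up to completing two sessions, which a cycle-1 progressor never does.

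A reader might infer more from the same passages. The documents do not support these readings:

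- **That the allocation phrase in Section 26 is an analysis error.** It is multi-arm wording, but with one arm it can only mean analysis as a Tb-161 patient, and keeping such patients in is sound.
- **That control achieved on another therapy would be credited to Tb-161.** A cut-off at new therapy is commonly left to the SAP, which is not at hand. Response scans are also tied to 4-6 weeks after each session, which leaves very little room for this.
- **That Section 24 contradicts Section 26 on alternative treatment.** Section 24 reads naturally as saying that no established alternative exists, and Section 15 says there is no standard of care for refractory disease.
- **That progressors are dropped from the DCR and replaced.** No passage says so.

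**Conclusion.** The concern holds in a limited form and is minor. Sections 15 and 26, together with the unconditional blood schedule, do not agree on whether a patient with PD after cycle 1 stays under observation. Taken literally, Section 15 can remove one of three post-cycle blood tests and all later toxicity for a selected group. DCR is untouched as long as these patients are counted in the 20 as failures.

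The number affected lies between 0 and the DCR failures, at most 2.6 of 20 expected at 87% and 6.6 of 20 at 67%. The blood-test loss assumes a scan before week 6 and exit at that scan. How much toxicity would be missed cannot be derived: it depends on how often late events occur after a single cycle, and the documents do not give this.

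**What to change.** Reconcile Sections 15 and 26 so that leaving protocol treatment is kept apart from leaving the study. Suggested content for Section 15: PD after cycle 1 ends protocol treatment only; the patient stays in the DCR denominator and is counted as not having disease control; the safety assessments and follow-up already scheduled continue unless the patient withdraws consent. Add a cross-reference in Section 26. Because Section 12(b) starts later follow-up after two sessions, also state how it applies to a patient who had only one.

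This concerns data collection and counting. It proposes no change to who receives a second session, to referral or to any later treatment.

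The cost is a wording amendment and the continued follow-up of a few patients at visits already in the schedule. Some of them will be under other care by then, so attribution of late events will be less clear. Section 15 already grades all events regardless of attribution, which limits that drawback.
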